8. RESEARCH QUESTION AND OBJECTIVES

COPD Patients usually do not only show respiratory symptoms, but also physical incapacity and several comorbidities^{XXIII}. These often result in impaired health status and reduced health-related quality of life and may lead to hospitalisations and increased mortality^{XXIV}. Amongst others, low lung function^{XXV}, frequent exacerbations^{XXVI} comorbidities^{XXVII} and a low level of physical activity are negative factors for health status in COPD. Physical exercise^{XXVIII} and pharmacological interventions may improving health status, as e.g. shown in the UPLIFT trial with tiotropium^{XXIX}.

The cross-sectional BOLD study assessed the impact of COPD on health status in a general population-based survey including almost 12000 subjects from 17 countries^{XXX}. 2269 COPD patients (defined by a post-bronchodilator forced expiratory volume in 1 s/forced vital capacity <0.70) were found to show lower physical component scores (44±10 vs. 48±10 units, p<0.0001) and mental health component scores (51±10 vs. 52±10 units, p = 0.005) than subjects without COPD. The effect of reported heart disease, hypertension and diabetes on physical health component scores (-3 to -4 units) was considerably less than the effect of COPD GOLD grade 3 (-8 units) or 4 (-11 units).

Dyspnoea was the most important determinant of low physical and mental health component scores. In addition, lower forced expiratory volume in 1 s, chronic cough, chronic phlegm and the presence of comorbidities were all associated with a lower physical health component score.

The authors conclude COPD to be associated with poorer health status but the effect to be stronger on the physical than the mental aspects of health status. Severe COPD had a greater negative impact on health status than self-reported cardiovascular disease and diabetes.

The contribution of physical inactivity to disability in COPD can be difficult to distinguish from disease progression^{XXXI}. However, it is clear that physical activity is significantly lower in patients with COPD than in healthy controls^{XXXII, XXXIII}.

COPD prevents patients from carrying out daily activities due to exercise intolerance, which is often attributed to limited pulmonary ventilation.

However, a number of observations have suggested that, for many COPD patients, other factors are involved, including deconditioning due to physical inactivity. This may be related to avoidance of exertion as a result of fear of dyspnoea. Furthermore, physical inactivity has been associated with skeletal muscle weakness and exercise intolerance^{XXXIV, XXXV}.

The loss of physical activity in COPD is also associated with increased mortality^{XXXVI}. Data from a study of 2386 patients with COPD demonstrated that, following adjustment for all relevant confounders, subjects who reported low, moderate or high physical activity had a significantly lower risk of all-cause mortality than those with very low physical activity (p = 0.001)^{XXXVII}.

Clinical studies^{XXXVIII, XXXIX, XL} of both Spiriva[®] and Striverdi[®] Respimat[®] in COPD patients have demonstrated significant improvement in exercise capacity^{XLI}.

The benefits of tiotropium + olodaterol FDC have been studied in controlled Phase III programs on exercise endurance, however, data regarding physical activity when treated with Spiolto[®] Respimat[®] is not available from a real world setting.

In the AKTIV! observational study the combination of Tiotropium plus Olodaterol showed improved physical functioning, translating into overall improved general condition in patients presenting with a broad COPD severity range within a short time frame^{XLII}. Thus, it is the first study to give a hint that the tiotropium + olodaterol combination may improve physical functioning and health condition.

Various questionnaires on quality of life and physical functioning are used to try assessing COPD patients' health status and physical state. The Clinical COPD questionnaire (CCQ) has been developed and validated in the Netherlands especially for COPD patients by Jan Kocks et al in 2006^{XLIII} to categorize patients' impairments generally and focus patients' treatment on their specific needs.

The CCQ is easy to apply. It takes less than 2 minutes to complete, is widely used to monitor COPD health status and control and consists of 10 questions, covering 3 domains: symptom domain (4 questions (#'s 1,2,5,6)); functional status domain (4 questions(#'s 7,8,9,10)) and mental status domain (2 questions (#'s 3,4)). The questionnaire is responsive to intervention and has been translated and validated in over 140 languages^{XLIV}. The CCQ thus is a very well-known and widespread questionnaire, which is also included in the GOLD guidelines and is validated also in German language. It has been given maximum ranking in "COPD wellness tools" overview by the International Primary Care Respiratory Group (IPCRG)^{XLV}.

8.1 STUDY OBJECTIVES

The objective of this NIS is to measure changes in health and functional status by the CCQ, in COPD patients receiving treatment with Spiolto[®] Respimat[®] after approximately 6 weeks in routine clinical practice.

Each of the 10 CCQ questions is scored by the patient on a 7-point scale between 0 and 6 at baseline and end of the observation after approximately 6 weeks. The sum of the scores divided by 10 gives the CCQ score, which measures the health and functional status. A higher CCQ score is indicative of worse status.

The functional status (CCQ-4) is calculation as the sum of the 4 questions (#'s 7, 8, 9, 10) divided by 4. A change of 0.4 points is considered to be the MCID for both CCQ score and CCQ-4.

Primary objective: Assess the proportion of patients achieving “therapeutic success” (= 0.4 point decrease in the CCQ score between baseline and approximately week 6).

Secondary objectives are assessment of changes in CCQ and CCQ-4 from visit 1 (baseline visit at the start of the study) to visit 2 (final visit at the end of the study, approx. 6 weeks after visit 1), the patient’s general condition (physician’s evaluation) at visit 1 and at visit 2, as well as patient satisfaction with Spiolto[®] Respimat[®] and willingness to continue treatment with Spiolto[®] Respimat[®] at visit 2 as proxy for adherence.

9. RESEARCH METHODS

9.1 STUDY DESIGN

This is a self-controlled non-interventional study (NIS), as referred to in §4.23 and §67.6 AMG, enrolling consented COPD patients who will be treated with Spiolto[®] Respimat[®] according to the approved SmPC.

9.2 SETTING

9.2.1 Study sites

It is planned that data of approximately 1300 patients from approximately 400 sites in Germany will be collected. Site selection will be performed to reflect routine COPD care in Germany in order to secure representativeness of the COPD population. A log of all patients included into the study (i.e. having given informed consent) will be maintained in the ISF at the investigational site irrespective of whether they have been treated or not.

9.2.2 Study population

Inclusion Criteria:

Patients can be included if all of the following criteria are met:

- Written informed consent prior to participation
- Female and male patients ≥ 40 years of age
- Patients diagnosed with COPD and requiring a combination of two long-acting bronchodilators (LAMA + LABA) according to approved SmPC and GOLD COPD guideline recommendation 2017 (GOLD COPD groups B to D)
- Treatment with Spiolto[®] Respimat[®] acc. to SmPC at the discretion of the physician.

Exclusion Criteria:

- Patients with contraindications according to Spiolto[®] Respimat[®] SmPC
- Patients already on a LABA/LAMA combination (free and fixed dose) in the last 6 weeks before study entry
- Patients continuing LABA-ICS treatment should not be additionally treated with Spiolto[®] Respimat[®] in order to avoid a double dosing of long-acting beta-agonists
- Pregnancy and lactation
- Current participation in any clinical trial or any other non-interventional study of a drug or device.

9.2.3 Study visits

Patients will be enrolled consecutively and will be followed over an observational period of approximately 6 weeks. Data as listed in [Table 9.2.3.1](#) will be collected.

Proprietary confidential information © 2017 Boehringer Ingelheim International GmbH or one or more of its affiliated companies

Two study visits will be performed. At Visit 1 (baseline) the patient will be included into the NIS. At visit 2, after approximately 6 weeks from baseline, the observation of the patient will end. The respective exams and data to be collected are listed in Table 9.2.3.1.

Table 9.2.3.1: Visit flow chart and data collection parameters

Parameter	Visit 1; baseline visit	Visit 2; approx. 6 weeks after baseline visit
Informed Consent	X	
Inclusion / Exclusion Criteria	X	
Patient demographics (age, gender, height, and weight)	X	
Start of COPD	X	
Number of exacerbations in the last 12 months	X	
Number of exacerbations leading to hospitalization in the last 12 months	X	
mMRC breathlessness scale, completed by the patient	X	
Past COPD therapies (6 weeks before visit 1)	X	
Respimat [®] training (yes/no)	X	
COPD severity based on GOLD assessment ¹	X	
GOLD spirometric classification, if available ²	X	
Smoking history	X	X
Concomitant diseases / Comorbidities	X	X
COPD related and other relevant concomitant medication	X	X
Health and functional status by CCQ questionnaire, completed by patient	X	X
General condition of patient evaluated by Physician's Global Evaluation (PGE)	X	X
Safety: Adverse Drug Reactions (serious and non-serious), fatal AE, pregnancy	X	X
Patient satisfaction with Spiolto [®] Respimat [®]		X
Rationale for Spiolto [®] Respimat [®] treatment discontinuation (if applicable)		X
Continuation or discontinuation of treatment with Spiolto [®] Respimat [®] after the study (yes/no)		X

¹ GOLD patient group (B, C or D) will be automatically calculated within the eCRF based on available exacerbation history and mMRC.

² GOLD stage 1-4 spirometric classification of airflow limitation based on post-bronchodilator FEV₁ if available.

9.2.4 Study discontinuation

Boehringer Ingelheim reserves the right to discontinue the study overall or at a particular study site at any time for the following reasons:

1. Failure to meet expected enrolment goals overall or at a particular study site
2. Emergence of any efficacy/safety information that could significantly affect continuation of the study, or any other administrative reasons, i.e. lack of recruitment
3. Violation of the observational plan or the contract by a study site or investigator, disturbing the appropriate conduct of the study

9.3 VARIABLES

The following parameters will be collected and assessed at visit 1 and/ or visit 2:

- Patient demographics (age, gender, height & weight)
- Smoking status (current smokers, former smokers, and never smokers) and pack-years
- Concomitant diseases / Comorbidities such as cardiovascular disease, diabetes mellitus, musculoskeletal impairment, renal diseases, liver diseases, osteoporosis, gastroesophageal reflux (GERD), or lung cancer
- COPD-related and other concomitant medication such as beta-blockers, beta-agonists, corticosteroids, or proton pump inhibitors
- Reported exacerbations based on medical history in the last 12 months and exacerbations leading to hospitalization in the last 12 months
- Assessment of the severity of breathlessness based on the Modified Medical Research Council Questionnaire (mMRC)
- Health and functional status based on CCQ scores
- Patient satisfaction with Spiolto[®] Respimat[®] to assess the overall satisfaction with Spiolto[®] Respimat[®] as well as specific inhalation from the device and device handling
- General condition of patient based on Physician's Global Evaluation (PGE) to assess the general condition of the patient at the beginning and at the end of the study
- Safety Reporting; Adverse Drug Reactions (serious and non-serious), fatal AEs, and pregnancies at the beginning and at the end of the study
- GOLD spirometric classifications (1, 2, 3, 4) and GOLD patient groups (B, C, D) based on GOLD guidelines 2017

9.3.1 Exposures

All patients will receive LAMA/LABA combination treatment with Spiolto[®] Respimat[®] according to the German SmPC.

Spiolto[®] Respimat[®] contains

- the long-acting anticholinergic tiotropium bromide.
The dose dispensed is 2.5 micrograms of tiotropium per puff, equivalent to 3.124 micrograms tiotropium bromide 1 H₂O. The dose dispensed is the quantity available to patients after crossing the mouthpiece.
- the selective beta₂-adrenoceptor agonist olodaterol. The dose dispensed is 2.5 micrograms of olodaterol per puff (as olodaterol hydrochloride). The dose dispensed is the quantity available to patients after crossing the mouthpiece.

The recommended daily dose of Spiolto[®] Respimat[®] for adults is 5 micrograms of tiotropium ion (tiotropium) plus 5 micrograms of olodaterol, equivalent to inhaling 2 puffs from the Respimat[®] inhaler once daily at the same time of day.

The Summaries of Product Characteristics on Spiolto[®] Respimat[®] is contained in the NIS ISF in the “Summary of Product Characteristics” section.

Note: The recommended doses stated in the Summary of Product Characteristics should not be exceeded.

9.3.2 Outcomes

9.3.2.1 Primary outcomes

“Therapeutic success” at visit 2 (0.4 -point decrease in the CCQ score from visit 1 to visit 2).

The primary outcome is not a safety outcome.

9.3.2.2 Secondary outcomes

- Changes in the CCQ and CCQ-4 score from visit 1 to visit 2
- General condition of the patient, evaluated by the physician (PGE score) at visit 1 and visit 2.
- Patient satisfaction with Spiolto[®] Respimat[®] at visit 2.
- Willingness to continue treatment with Spiolto[®] Respimat[®] at visit 2 as proxy for adherence

The secondary outcomes are not safety outcomes.

9.4 DATA SOURCES

Medical records collected through routine clinical care will be used to assess the inclusion/exclusion criteria of patients. Such medical records will be used for patient demographics, smoking history, collection of previous COPD medication, concomitant diseases, and concomitant medication.

All patients will be enrolled consecutively.

The treating physician will use the Physician's Global Evaluation (PGE) to evaluate the general condition of the patient on an 8-point ordinal scale from 1 (very poor) to 8 (excellent). PGE will be completed before and approx. 6 weeks after treatment initiation. The modified Medical Research Council (mMRC) scale will be used to assess the breathlessness state of the patient before the treatment. The mMRC stage (0 to 4) collected from the patient as well as the exacerbation history will be used to automatically calculate the GOLD patient group (B, C, or D) in the eCRF.

The CCQ questionnaire contains 10 questions about everyday physical activity and functioning. Each question can be scored by patients on a 7-point scale between 0 and 6. The sum of the scores divided by 10 gives the CCQ score, which measures the health and functional status. For the functional status calculation the sum of the 4 questions (# 7, 8, 9, 10) is divided by 4. A change of 0.4 points is considered to be the MCID. This questionnaire will be filled out by the patient and entered into the database. Patients will be asked to complete the CCQ in order to evaluate their health and functional status before and after treatment with Spiolto[®] Respimat[®].

A patient satisfaction survey will also be completed at visit 2, using a 7-point ordinal scale with divisions from very dissatisfied to very satisfied.

Willingness to continue treatment is assessed by a yes/no question.

9.5 STUDY SIZE

We assume that patients treated with Spiolto[®] Respimat[®] will have a CCQ therapeutic success rate similar to the SGRQ responder rate. In the TONADO studies^v patients treated with Spiolto[®] Respimat[®] had a 57.5% SGRQ responder rates after 24 weeks.

The TONADO was a selected trial population, so a real world population would probably show somewhat lower numbers due to the wide diversity of potential patients that will be followed up. Therefore a 50% CCQ therapeutic success rate is a reasonable assumption.

Assuming a 50% therapeutic success rate for CCQ and a sample size of 1170 patients, the 95% confidence interval for the therapeutic success rate would be between 47.1% (lower limit) and 52.9% (upper limit).

Subgroups with long acting bronchodilators at baseline (i.e., LABA only, LAMA only, LABA and ICS) will be analyzed only if they include more than 20% of all patients. In the smallest subgroup (with at least 234 patients), assuming a 50% therapeutic success rate, the 95% confidence interval would be between 43.6% and 56.4%.

To account for a 10% drop-out rate, the sample size becomes 1300 patients.

9.6 DATA MANAGEMENT

A data management plan (DMP) will be created to describe all functions, processes, and specifications for data collection, cleaning and validation. The electronic Case Report Forms (eCRFs) will include programmable edits to obtain immediate feedback if data are missing (also negative answers, unknown), out of range, illogical or potentially erroneous. These rules may encompass simple checks such as range validation or presence/absence of data.

Concurrent manual data review may be performed based on parameters dictated by the DMP. Ad hoc queries to the sites may be generated and followed up for resolution. A source data quality audit may be initiated to ensure that the data in the database is accurate. Source data verification (SDV) will be performed at sites identified by a risk-based approach as needed.

The database will be housed in a physically and logically secure computer system maintained in accordance with a written security policy. The system will meet the standards of the International Committee on Harmonization guideline E6R1 regarding electronic study data handling and the safety requirements of the FDA (US Food & Drug Administration) concerning systems for the data acquisition of clinical studies in accordance with "Title 21 Code of Federal Regulations (21 CFR Part 11): Electronic Records; Electronic Signatures. Patient confidentiality will be strictly maintained.

9.6.1 Data Entry / EDC

Data entry into the eCRF follows the instructions in the EDC system user manual and is further supported by help and hint texts. Support documents will also be provided within the online system documents which give explanations to basic functions and field types in the eCRF.

With data entry into the EDC system, all changes and user information will be saved in an audit trail.

The data review and validation steps for a project are defined in the data validation plan (DVP).

The DVP includes all definitions of electronic checks and the defined manual checks, which will be performed directly in the EDC system or can be based on listings.

Electronic edit checks (eChecks) are performed automatically and directly when entering data into the eCRF. Missing data entries or implausibilities are indicated to the user immediately.

Manual Checks are applied to verify the entered data validity and plausibility.

Queries can result from various sources:

- Manual Checks by data management
- Manual Checks by pharmacovigilance
- Source data verification during on-site monitoring

9.6.2 Source Documents

The source documents are contained in the patient's medical record. Data collected on the eCRFs must be traceable to these source documents in the patient's medical records as far as this is routine documentation. All original source documentation is expected to be stored at the site for the longest possible time required by local applicable regulations. The site will be instructed to notify the Sponsor before any destruction of medical records of study participants.

9.6.3 File Retention and Archiving

The study database and all study-specific documents received by _____ will be transferred to BI regularly during and after the study period. Archiving will be performed by BI Pharma in accordance with BI SOPs.

To enable evaluations and/or audits from regulatory authorities or the Sponsor, the investigator agrees to keep records, including the identity of participating patients, copies of all CRFs, SAE forms, source documents and adequate documentation of relevant correspondence (e.g., letters, meeting minutes, telephone calls reports). The records should be retained by the investigator according to local regulations, or as specified in the study contract, whichever is longer.

Each site will receive a study site file at study initiation which contains all documents necessary for the conduct of the study and is updated throughout the study. This file must be available for review in the event the site is selected for monitoring, audits, or inspections and must be safely archived for at least ten years after the completing participation in the study. In the event that archiving of the file is no longer possible at the site, the site will be instructed to notify the Sponsor.

9.7 DATA ANALYSIS

Planned analyses

More details will be described in the statistical analysis plan (SAP).

No formal hypothesis testing will be performed since this is a self-controlled study.

All patients who have received at least one dose of Spiolto[®] Respimat[®] will be included in the analysis; this is the treated set. All analyses will be performed on the treated set (as-treated analysis). If patients have missing values for an outcome, those patients will be excluded for that outcome's analysis. For example, if a patient is missing the CCQ score at Visit 1 and/ or Visit 2, that patient will be excluded from the analyses for the primary endpoint of therapeutic success and the secondary endpoint of change in CCQs from Visit 1 to Visit 2.

The assessment will be carried out using SAS[®] software. The statistical characteristics presented in the end-of-text tables will be N / mean / SD / min / median / max for continuous

variables. Tabulations of relative and absolute frequencies will be presented for categorical variables. Incidence rates and 95% CI will be given when appropriate.

The analyses will relate to the following data:

- Patient demographics (gender, age, height, weight)
- Comorbidities (main diagnosis and concurrent diagnosis according to MedDRA, version valid as at the time of database closure)
- COPD related and other concomitant medication (according to the WHO classification, version valid at the time of database closure)
- History of smoking
- Reported exacerbations
- Breathlessness based on mMRC score at visit 1
- Therapeutic success based on CCQ score; primary outcome
- Changes from Visit1 to Visit 2 in the CCQ and CCQ-4 score; secondary outcome
- Patient satisfaction with Spiolto[®] Respimat[®] at visit 2 only; secondary outcome
- General condition of the patient: evaluated by the physician (Physician's Global Evaluation (PGE)), secondary outcome
- Willingness to continue; secondary outcome
- Adverse Drug Reactions (ADR & SADR), fatal AEs, pregnancies
- GOLD spirometric classifications (1, 2, 3, 4) and GOLD patient groups (B, C, D)
- Details of treatment with inhaled respiratory agents before the study
- Details of treatment with respiratory agents during the study
- Reasons for ending treatment during the observation period
- Details of treatment continuation / discontinuation

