**2.5 Tables for subgroup analysis**

For each of the following subgroups

- Maintenance naïve patients vs. patients already treated at baseline (i.e. before start of therapy with Spiolto® Respimat®) with long-acting bronchodilators (LAMA only or LABA only) or LABA+ICS [Only if both categories include more than 20% of all patients, respectively]
- Maintenance naïve patients vs. patients already treated at baseline with long-acting bronchodilators (LAMA only) vs patients already treated at baseline with long-acting bronchodilators (LABA only) vs patients already treated at baseline with long-acting bronchodilators (LABA+ICS)
- ICS treatment at baseline (Patients with ICS vs. Patients without ICS) [Only if both categories include more than 20% of all patients, respectively]
- GOLD spirometric classifications (Group 1) (1/2 vs. 3/4)
- GOLD spirometric classifications (Group 2) (2 vs. 3 vs. 4)
- GOLD patients group (Group 1) (B vs. C/D)
- GOLD patients group (Group 2) (B vs. C vs. D)
- Age (≤ 65 years vs. >65 years)
- Exacerbations in the last 12 months (≤1 vs. ≥2)
- Hospitalizations due to exacerbations (0 vs. ≥1)
- Smoker (Smoker vs. Ex-Smoker vs. Non-smoker)
- Patients with cardiac comorbidities (No vs. Yes)
- Continuation of Spiolto® Respimat® usage after end of study observation (No vs. Yes)

Table 1 to Table 9 given below will be displayed for each subgroup, respectively, subgroup and group 1, group ... are respective placeholders.

Primary endpoints

**Subgroup analysis- Table 1: Analysis stratified by subgroup- Full Analysis Set- Total CCQ score- Share of patients with therapeutic success after 6 weeks (approximately), defined as 0.4-point decrease of total CCQ score between baseline and week 6 (approximately)**

CCQ		N	%	CI 95%
Share of patients with therapeutic success				
Group 1	Therapy successful			
	Therapy not successful			
	Missing			
	Total			
Group ...	Therapy successful			
	Therapy not successful			
	Missing			
	Total			
Total	Therapy successful			

CCQ		N	%	CI 95%
Share of patients with therapeutic success				
	Therapy not successful			
	Missing			
	Total			

**Subgroup analysis- Table 2: Analysis stratified by subgroup- Full Analysis Set- Total CCQ score- Share of patients with therapeutic success-  $\chi^2$ -Test (Fisher's Exact test)**

X  -Test (Fisher's Exact test) - Therapy success	p-Value
Group 1 vs. Group ...	

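### SAP 2.5 omits the protocol's 20% condition from the four-way prior-therapy split and uses a Visit 2 outcome, continuation of treatment, as an efficacy subgroup

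*Protocol*

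**What the plan says.** **Prior therapy.** Protocol 9.5 names three groups by long-acting treatment at baseline (LABA only, LAMA only, LABA and ICS) and says that they "will be analyzed only if they include more than 20% of all patients". It then gives a 95% interval of 43.6% to 56.4% for the smallest subgroup, put at 234 patients or more.

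SAP 2.5 lists 13 subgroup variables. The first (maintenance-naïve against all pretreated, pooled) and the third (ICS yes or no) carry the restriction "Only if both categories include more than 20% of all patients, respectively". The second compares four groups: naïve, LAMA only, LABA only, and LABA+ICS. It contains the words "vs patients already treated at baseline with long-acting bronchodilators (LABA only) vs patients already treated at baseline" and ends with no size restriction.

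**Continuation.** The last variable in SAP 2.5 is Spiolto Respimat "usage after end of study observation (No vs. Yes"). In Protocol Table 9.2.3.1 the row beginning "Continuation or discontinuation of treatment with Spiolto" is marked for Visit 2 only. Protocol 9.3.2.2 lists willingness to continue "at visit 2 as proxy for adherence" among the secondary outcomes. SAP Table 15.2.1 6 reports it as an outcome, from a field of the Visit 2 dataset.

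**Testing.** Protocol 9.7 says "No formal hypothesis testing will be performed since this is a self-controlled study". SAP 2.5 says "Table 1 to Table 9 given below will be displayed for each subgroup", and Tables 2, 5, 7 and 9 of that set contain p-values. Sensitivity Table 4 in SAP 2.3 contains one more.

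**The concern.** The protocol sets a minimum size for three named groups so that none is reported with less precision than it states. The SAP applies a 20% rule to a pooled version of those groups and to ICS use, but not to the split that shows them one by one. The report could then give success rates and p-values for categories that the protocol excludes as too small.

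Continuation raises a different problem. A subgroup is meant to describe patients before the response is known. Here both the classifier and the response are established at Visit 2, and a patient who felt no benefit may choose to stop for that reason. SAP Table 15.2.1 7 lists adverse events and the patient's wish among the reasons for stopping. A higher success rate in those who continue could simply mean that responders stay on treatment. Because the full table set is repeated for every variable, Visit 2 PGE and satisfaction are also tested by continuation.

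**Working it through.** **1. The protocol's precision figures.** Inputs from Protocol 9.5: success p = 0.50, n = 1170, smallest subgroup 234. Half-width = 1.96 × √(p(1 − p)/n).

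- n = 1170: 1.96 × √(0.25/1170) = 2.9 points, so 47.1% to 52.9%. This matches the protocol.
- 0.20 × 1170 = 234: 1.96 × √(0.25/234) = 6.4 points, so 43.6% to 56.4%. This matches the protocol.

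**2. Without the condition.** The documents do not give the shares of the prior-therapy categories. The 10% and 5% shares below are assumptions.

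| Share of 1170 | n | 95% half-width at 50% success |
|---|---|---|
| 20% (protocol minimum) | 234 | 6.4 points |
| 10% (assumed) | 117 | 9.1 points |
| 5% (assumed) | 58 | 12.9 points |

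This arises in two ways.

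- *Large pretreated group, one small category.* The pooled split is shown, and a category such as LABA only, at 10% say, is analysed and tested although Protocol 9.5 would exclude it.
- *Pretreated patients at or below 20% in total.* With 234 or fewer, the first variable's restriction suppresses the pooled comparison. The second variable still divides the same patients into three, so at least one category has 234/3 = 78 patients or fewer. The half-width at 78 is 1.96 × √(0.25/78) = 11.1 points.

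**3. Timing of continuation.** The protocol flow chart records it at Visit 2 only. The protocol outcome list and SAP Table 15.2.1 6 both treat it as an outcome. SAP 2.5 uses it as a classifier for CCQ success, which is also fixed at Visit 2.

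How far this could separate the two groups depends wholly on assumption. Take 50% success and 90% continuing overall:

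- If continuation is unrelated to response, the gap in success is 0.
- If 92% of responders and 88% of non-responders continue, success is 0.46/0.90 = 51.1% among continuers and 0.04/0.10 = 40.0% among stoppers, a gap of 11.1 points.
- If the figures are 95% and 85%, success is 0.475/0.90 = 52.8% against 0.025/0.10 = 25.0%, a gap of 27.8 points.

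These show the mechanism and are not estimates for this study.

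**4. Number of p-values.** Per variable: success 1 (Table 2), change in CCQ-4 and total CCQ 2 (Table 5), PGE at two visits 2 (Table 7), satisfaction items 3 (Table 9). The total is 8.

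- All 13 variables: 13 × 8 = 104.
- Both conditional variables suppressed: 11 × 8 = 88.
- SAP 2.3, Sensitivity Table 4, adds 1.

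**The case against.** **On the 20% rule.** The protocol leaves detail to the SAP, and its wording could mean the three groups taken together, which is how the SAP's first variable applies it. But the protocol goes on to size the smallest subgroup at 234 or more, which favours a category-by-category reading. On the pooled reading the four-way split still conflicts, because it has no condition at all. Leaving detail to the SAP does not allow it to drop a stated condition.

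It is also fair to say that a pretreated share of 20% or less looks unlikely. Protocol 7.1 describes dual bronchodilation in groups B and C as an escalation from earlier long-acting treatment. One small category inside a large pretreated group is the more plausible case.

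**On testing.** A reader might infer that the SAP breaches the protocol's exclusion of hypothesis tests. The documents do not support that. The protocol rules out formal testing, and the SAP sets no significance level, hypothesis or decision rule, so its p-values can be read as descriptive. For the same reason, a count of expected false positives would assume a decision rule that the SAP does not contain. What stands is that nothing in the SAP states the status of these p-values.

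A reader might also count all pairwise comparisons, 24 × 8 = 192 in SAP 2.5. The pairing of Wilcoxon with Kruskal-Wallis makes one overall test per variable the natural reading.

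**On other inferences.** SAP Listing 5 puts continuation under a field of the baseline dataset. That could suggest it is being treated as a baseline variable, but the column is correctly titled and the field name looks like a clerical slip. The baseline PGE comparisons are not an error either: these groups are not randomised, so a baseline comparison gives context.

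**Conclusion.** The point holds for two rules in SAP 2.5. The four-way prior-therapy split lacks a condition that Protocol 9.5 states for the same groups. Continuation is a Visit 2 outcome and cannot serve as an efficacy subgroup.

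The first fault costs precision: a half-width of 9.1 or 12.9 points at assumed category sizes of 117 and 58, against 6.4 at the protocol's minimum. These figures rest on 1170 evaluable patients, 50% success and the category-by-category reading of the 20% rule. For the second, the documents give no basis for a size, and none is claimed.

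The missing status of 88 to 104 p-values in SAP 2.5, plus one in SAP 2.3, is a labelling gap and not a breach of the protocol. The primary success rate and its interval are unaffected. The SAP should be corrected, but the main result does not depend on it.

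**What to change.** 1. In the second variable of SAP 2.5, apply the protocol's condition to each pretreated category separately. Show any category at or below 20% of all patients as a count only, with no success rate, interval or test. If none of the three exceeds 20%, do not run the split.
2. Remove continuation from the efficacy subgroup list. Alternatively, tabulate continuation by therapeutic success, without a p-value, and describe it as an association between two Visit 2 outcomes.
3. State in SAP 2.3 and 2.5 that the between-group p-values are exploratory and unadjusted for multiplicity.

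The cost is a short SAP revision with no new data. The sponsor gives up results for pretreated categories at or below 20%, and the 8 p-values by continuation, which brings the maximum in SAP 2.5 from 104 to 96.
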